3.1 INCLUSION CRITERIA

In order to be eligible to participate in this study, a participant must meet all of the following criteria:

- Provide signed and dated informed consent
- Male or female, aged 18-65
- Diagnosed with nonspecific chronic low back pain by clinician, normal MRI if they had imaging done
- BMI is less than 30
- Suffered from chronic pain for > 6 months
- Self-report pain measures (VAS) >4
- Meets criteria for low depression and suicide risk as defined by the HAM-D
- 1 month free anticonvulsant medications, 48 hours of opioids and benzodiazepines (can take over the counter pain killers)
- Can be taking over the counter pain killers not day of session (Refrain from taking over the counter medications such as antihistamines, albuterol, nasal decongestants for one week prior to stimulation sessions)
- Capacity to understand all relevant risks and potential benefits of the study (informed consent)
- Willing to comply with all study procedures and be available for the duration of the study
- Women of reproductive potential must test negative on a pregnancy test prior to start of treatment
- Speak and understand English

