5.1.2 INITIAL SCREENING SESSION (VISIT 1)

At day 1 of stimulation, participants will be guided through the consent form and the HIPAA authorization form and be given the time to ask any questions about the information discussed. To ensure that all aspects of the research are understood, participants may be asked a series of questions about the research they are about to take part in (*Appendix E*). Once it is clear that the participant understands the consent form and HIPAA authorization, they may sign the forms.

Following the consent process, the participant completes the ODI and DVPRS to measure disability and pain intensity on 0-11 scale. The HAM-D and DASS-21 will assess low suicide risk and depression level. The self-report measures: UCLA Activity Score, PCS, and PSEQ will assess physical activity limitations, pain experience, and confidence in daily activities. Data on demographics, handedness, stai, bis-bas, and opinion pre-treatment will also be collected.

Once eligibility has been confirmed and all relevant data collected, Day 1 of stimulation will begin.

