5.2 STIMULATION SESSIONS

5.2.1 DAY 1 OF STIMULATION (VISIT 1 CONTINUED)

Prior to starting any study procedures, female participants will be asked to take a urine pregnancy test to ensure continued eligibility. The 5xSST, FTF, and pressure pain threshold test will be administered before stimulation. A resting state EEG will be recorded for 5 min before and after stimulation. The participant will receive 40 minutes of sham or 10 Hz tACS stimulation (as per the initial randomization) while watching “Reefscape”. The stimulation will be followed by the pressure pain threshold, 5xSST, FTF, stimulation adverse effects questionnaire and perceived improvement ending the session.

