5.2.2 DAYS 2 OF STIMULATION (VISIT 2)

Prior to starting any study procedures, female participants will be asked to take a urine pregnancy test to ensure continued eligibility. The ODI, DVPRS, 5xSST, FTF, and pressure pain threshold test will be administered before stimulation. A resting state EEG will be recorded for 5 min before and after stimulation. The participant will receive 40 minutes of sham or 10 Hz tACS stimulation (as per the initial randomization) while watching “Reefscape”. The stimulation will be followed by the pressure pain threshold, 5xSST, FTF, stimulation adverse effects questionnaire and perceived improvement ending the session.

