5.3 FOLLOW-UP

5.3.1 FOLLOW-UP EMAIL

Two days after both sessions of stimulation, participants will receive an email with a follow up survey to assess any change in pain perception. The ODI and DVPRS will take approximately 15 minutes to complete.

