11 STATISTICAL PLAN

11.1 STATISTICAL ANALYSIS STRATEGIES

Our study design is a AB/BA crossover and we will ensure a washout effect by scheduling 1-3 weeks between stimulation sessions. A continuous outcome approach will be used to analyze the crossover trial data where carryover effects will be assumed to be equal.

Primary outcome: Use kubios software to analyze HRV over before and after stimulation. A standard spectral analysis will be applied to the pre and post intervals, including total power, HF, LF, and HP. Specifically looking at the HF component since it reflects the parasympathetic modulation of the heart rate. Use a repeated measure ANOVA with factor session (1 vs 2) and factor treatment (active vs sham) (R software). We hypothesize a treatment main effect and with no session effect and no interaction.

Secondary outcome: A Mann-Whitney-Wilcoxon rank-sum testMann Whitney U test (R software) will be performed on the self-report VAS pain scale (nonparametric scale) (from DVPRS) before and after stimulation as well as between sessions to analyze any differences in self-report perceived pain. Grouped ANOVAs and unpaired t-tests may also be used to analyze correlations within other self-report measures

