APPENDIX A: SCHEDULE OF EVENTS

A detailed schematic describing all visits and assessments.

	Phone Screening	First Stimulation (Sham or 10 Hz)	2 Days Later	Second Stimulation (Sham or 10 Hz)	2 Days Later
Procedures					
Provide Verbal Consent	x				
Signed Consent Form		x			
Signed HIPAA Authorization		x			
Assessment of Eligibility Criteria	x	x			
Review of Medical History	x	x			
Review of Concomitant Medications	x	x			
Baseline Assessments (list assessments)		x			
Clinical Assessments		x		x	
Pressure Pain Threshold Test		x		x	
Urine Pregnancy Test		x			
Randomization		x			
Stimulation		x		x	
Stimulation Questionnaire, Perceived Improvement Questionnaire, HAM-D		x		x	
Email Questionnaires (Follow-up)			x		x

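### The Day 1 pain rating appears to be both the >4 entry test and the session 1 baseline, while the session 2 baseline has no threshold, so regression to the mean biases baseline-versus-active pain change

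*Combined protocol and SAP*

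**What the plan says.** Entry requires "Self-report pain measures (VAS) >4" (section 3.1; the study summary gives the same threshold).

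On Day 1, in the screening part of Visit 1: "Following the consent process, the participant completes the ODI and DVPRS to measure disability and pain intensity on 0-11 scale" (section 5.1.2). Stimulation follows on the same visit: "Once eligibility has been confirmed and all relevant data collected, Day 1 of stimulation will begin". Section 5.2.1 lists the Day 1 tests before stimulation without the DVPRS: "The 5xSST, FTF, and pressure pain threshold test will be administered before stimulation". Section 5.2.2 does list it before session 2: "The ODI, DVPRS, 5xSST, FTF, and pressure pain threshold test will be administered before stimulation".

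In Appendix A the row "Assessment of Eligibility Criteria" is marked at phone screening and first stimulation, and not at second stimulation. The telephone script in Appendix G contains no pain rating. The after value comes from the emailed survey (ODI and DVPRS): "Two days after both sessions of stimulation, participants will receive an email with a follow up survey to assess any change in pain perception" (section 5.3.1).

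Section 11.1 plans a rank-sum test on the "self-report VAS pain scale (nonparametric scale) (from DVPRS) before and after stimulation", and also between sessions. A session factor appears there only in the ANOVA for the primary heart rate variability outcome. The secondary hypothesis in section 2.4.1 compares baseline with active stimulation, not active with sham. Section 4.1.1 describes randomised stimulation codes and states no balancing of order.

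**The concern.** If one rating both admits people and serves as their baseline, those who happened to rate high that day are over-represented, and their next rating is lower on average whatever was done to them. Session 2 has a fresh rating that nobody must pass, so its before-after change lacks this component. The two sessions' changes are then not comparable.

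The secondary hypothesis is exposed because it sets active stimulation against baseline, so the sham session does not remove the artefact. The pain test has no session term that could absorb it. Section 11.2 says the results will be used to set sample sizes for later trials, so an inflated before-after change could carry forward into that planning.

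**Working it through.** The plan gives no SD, reliability or expected change for pain, so there is no figure of its own to reproduce.

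**Which rating is which.** Entry needs a score above 4 (3.1). The first scheduled pain rating is the Day 1 DVPRS (5.1.2); it is not repeated before session 1 (5.2.1), and the phone script has none. The outcome VAS comes from the DVPRS (11.1). The Day 1 DVPRS is therefore the only available session 1 before value, and the only scheduled rating to which the entry criterion could be applied.

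**Formula.** Let unselected ratings have mean m, between-person SD b, within-person SD w and independent errors. Put SD = √(b² + w²) and c = (4 − m)/SD. With selection on the first rating above 4 and no treatment effect, the expected fall to the next rating is

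fall = (w²/SD) × φ(c)/[1 − Φ(c)].

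Both session 2 ratings come after selection, so their expected difference is 0.

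**Assumptions, not in the documents:** m 4.5-5.5, b 1.2-1.5, w 1.0-1.5.

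- Largest fall (m 4.5, b 1.2, w 1.5): SD = √3.69 = 1.921; c = −0.260; φ/(1 − Φ) = 0.3857/0.6027 = 0.640; fall = (2.25/1.921) × 0.640 = 0.75.
- Smallest fall (m 5.5, b 1.2, w 1.0): SD = √2.44 = 1.562; c = −0.960; ratio = 0.2516/0.8315 = 0.303; fall = (1.00/1.562) × 0.303 = 0.19.

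On an integer scale, above 4 means 5 or more, a stricter cut. Simulation of 2,000,000 people per setting, with ratings rounded to 0-10, gives 0.29-0.97 over the same grid. The share rating 4 or below at session 2 with no treatment effect is 15-37%.

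**Sensitivity.**

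- At m 6.5 with the same SDs, the integer fall is 0.14-0.34.
- Over a wider continuous grid (mean 4-7, total SD 1.5-2.5, test-retest correlation 0.5-0.9) it is 0.01-1.0.
- Persistent fluctuation shrinks it, because the after rating comes only two days later. At mean 5, total SD 2, correlation 0.5, integer scale, the session 1 fall is 0.67 with independent errors, and 0.34 and 0.18 with fluctuation time constants of 3 and 7 days. The remainder reaching session 2 is at most about 0.06.

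**What reaches each contrast.** Let d be the session 1 fall.

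- *Pooled baseline versus active, each session with its own baseline, 10:10 order.* Half the active sessions are session 1, so the bias is d/2: 0.29/2 = 0.15 to 0.97/2 = 0.49 points, or 7-24% of the 2-point MCID in section 6.1.
- *Baseline read as the Day 1 rating.* The bias is d, 0.29-0.97.
- *Active minus sham change.* With k of 20 receiving active first, the bias is d × (2k − 20)/20. It is 0 at 10:10. At 7:13 it is 0.3d in size: 0.09-0.29 points. If order were assigned by simple randomisation, a 7:13 or worse split has probability 0.26.

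**False-positive rates.** These are simulated at nominal 5% with 20 participants, 10:10 order, means 5-6, total SD 2, correlations 0.5-0.8 and integer scale. For active sessions against their own baselines, the unpaired rank-sum test gives 0.2-4%, because it ignores the pairing; a paired signed-rank test gives 5-11%. A rank-sum before-after test of all 20 in session 1 gives 0.3-18%. The same range applies if the Day 1 rating is everyone's baseline, because with independent errors the expected fall is then the same.

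**The case against.** **The identity is inferred.** No section says that the entry VAS is the Day 1 DVPRS score. Section 5.1.1 mentions two phone assessments without naming them, and Appendix A also marks eligibility at the phone stage. This stands as a reason to write *appears to*. The inference is still strong, since no other pain rating is scheduled before session 1.

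**The size is uncertain.** Means of 4.5-5.5 lie close to the cutoff, and the assumed SDs imply correlations of only 0.39 (1.44/3.69) to 0.69 (2.25/3.25). A higher mean, or fluctuation lasting days, gives a smaller fall. This stands, and the range has to be reported with its assumptions.

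**Stronger readings.** A reader might infer that:

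- *The whole fall counts as an active effect.* Under balanced order only about half does, unless baseline means the Day 1 rating.
- *The sham comparison is biased too.* On average it is not when order is balanced.
- *False-positive claims will be common.* For the pooled contrast the planned test stays below 5%. Only the Day 1-baseline reading, or a separate session 1 test, exceeds that, and only in the least favourable settings.
- *Session 2 is wholly free of the artefact.* A small remainder can reach it.

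**Context.** The primary outcome is heart rate variability, which is not selected on pain, and this is a pilot without a sample size calculation. That limits the consequence, but a bias in a stated hypothesis that costs little to remove is still worth removing.

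**Conclusion.** The point holds as a modest, structural bias in a secondary endpoint. On the natural reading of the schedule, the rating that selects participants is also the session 1 baseline, and session 2 has no matching selection. With no treatment effect the expected session 1 fall is 0.29-0.97 points on the integer scale (0.19-0.75 continuous) at assumed means of 4.5-5.5, and 0.14-0.34 at mean 6.5. About half enters the pooled baseline-versus-active estimate if order is balanced.

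The direction follows from the design; the size rests on means, SDs and error independence that the documents do not give. In all settings examined the fall is below the MCID. The evidence supports a biased estimate of change. It does not support a claim that the active-sham comparison is invalid.

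**What to change.** 1. **Separate selection from baseline.** Add a 0-10 back-pain rating to the telephone script (Appendix G), apply the existing >4 criterion to that rating, and say so in section 3.1. Take the Day 1 DVPRS afterwards as a baseline with no threshold, as in session 2.

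2. **Change the pain analysis in section 11.1.** Make it a within-person active-versus-sham comparison of change with a session term, and align the secondary hypothesis in section 2.4.1. A rank-based form is available: compare each person's session 1 minus session 2 change between the two orders with a rank-sum test. Report baseline-versus-active change as descriptive only.

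The first change costs one phone question. Its downside is that about 15-37% (0.15 × 20 = 3 to 0.37 × 20 ≈ 7 of 20) may rate 4 or below on Day 1 and have less room to improve; the same share is already expected at session 2. The plan sets no maximum interval between call and visit, and medication use may differ at the call, so who enters could shift somewhat; recording the date of the phone rating would show the interval. If fluctuation persists and the call is close to Day 1, a small fall may remain, which the session term absorbs. The second change costs only text.

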2.4.1 SECONDARY OBJECTIVE

NULL HYPOTHESIS. There is no difference in self-reported perceived pain rating between baseline and the active stimulation.

ALTERNATIVE HYPOTHESIS. There is a difference in self-reported perceived pain rating between baseline and active stimulation.

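### The stated pain comparison runs from a rating day with over-the-counter painkillers barred to one with them allowed, without sham, so pain can fall with no tACS effect

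*Combined protocol and SAP*

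**What the plan says.** Section 3.1 permits over-the-counter painkillers with one restriction: "Can be taking over the counter pain killers not day of session".

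The pain ratings are scheduled as follows.

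- Visit 1 (5.1.2), on the first stimulation day: "Following the consent process, the participant completes the ODI and DVPRS". Stimulation comes afterwards.
- Visit 2 (5.2.2): "The ODI, DVPRS, 5xSST, FTF, and pressure pain threshold test will be administered before stimulation".
- After stimulation (5.2.1, and the same list in 5.2.2): "The stimulation will be followed by the pressure pain threshold, 5xSST, FTF, stimulation adverse effects questionnaire and perceived improvement ending the session". The DVPRS is not in the list.
- Follow-up (5.3.1): "Two days after both sessions of stimulation, participants will receive an email with a follow up survey to assess any change in pain perception". The survey consists of the ODI and DVPRS, and no painkiller rule is attached to it.

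The alternative hypothesis under the Secondary Objective in 2.4 reads: "There is a difference in self-reported perceived pain rating between baseline and active stimulation". The null has the same form, and neither mentions sham.

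Section 11.1 plans a Mann-Whitney-Wilcoxon rank-sum test that "will be performed on the self-report VAS pain scale (nonparametric scale) (from DVPRS) before and after stimulation as well as between sessions". It does not say whether the between-session part means active against sham or first against second session, nor whether it uses changes or raw scores. For the primary outcome, the same section treats session and treatment as different things: "factor session (1 vs 2) and factor treatment (active vs sham".

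Section 12.5 says concomitant medications are entered in REDCap but gives no timing at the two-day survey. Appendix A marks their review only at the phone screen and first session. That table also omits the visit 2 pregnancy test required by 5.2.2, so it is weak evidence.

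**The concern.** The stated contrast starts at a rating made without that day's painkiller and ends at one made with painkillers freely available. Whether baseline means the visit 1 rating or the rating before the active session, it falls on a session day. Anyone who returns to usual painkillers by the survey moves the contrast downward, in the direction of benefit. Regression to the mean (entry requires VAS above 4) and placebo response act in the same direction.

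Each painkiller rule is reasonable by itself. The difficulty is a contrast that spans both without the sham session that every participant also completes. Section 11.2 says the results will determine sample sizes for later trials, so a biased fall could carry forward even if no test rejects. The point covers over-the-counter painkillers only.

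**Working it through.** **Inputs from the documents.** n = 20 (section 3), DVPRS MCID of 2 points (6.1), entry VAS above 4 (3.1). Section 11.2 makes no sample size calculation, so there is no figure of the plan to reproduce.

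**Step 1. Line up the ratings.**

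| DVPRS rating | Timing | Over-the-counter painkillers |
|---|---|---|
| Visit 1, before stimulation | session day | barred |
| Visit 2, before stimulation | session day | barred |
| Same day, after stimulation | none listed | – |
| Email survey | two days after each session | no rule |

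**Step 2. Size of the spurious fall.** If painkillers lower the score by *e* points and a fraction *p* of participants have resumed them, the mean fall with no tACS effect is *e* × *p*. Both inputs are assumed: *e* from 0.5 to 1.5 and *p* from 0.3 to 0.9.

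- Low: 0.5 × 0.3 = 0.15 points
- Middle: 1.0 × 0.6 = 0.60 points
- High: 1.5 × 0.9 = 1.35 points

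**Step 3. False rejection of the baseline-versus-active test.** 10,000 simulated trials per scenario, n = 20, bivariate normal scores, assumed SD of change 2, two-sided 0.05. The SD of a single score is 2/√(2(1 − ρ)): 2.0 at ρ = 0.5 and 2.58 at ρ = 0.7. Rates are given as ρ = 0.5 / 0.7.

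| Shift | Planned unpaired rank-sum | Paired t-test |
|---|---|---|
| none | 0.8% / 0.2% | nominal 5% |
| 0.15 | 1.1% / 0.2% | 6.2% / 5.9% |
| 0.60 | 7.5% / 2.3% | 23.2% / 24.1% |
| 1.35 | 52% / 27% | 79.1% / 79.9% |

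The planned test rejects less often because it treats paired ratings as independent. Pairing it without adding sham would make false rejection worse.

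A second set of assumptions (integer 0–10 scores, mean 5.5, SD 1.8) applied shifts of 0.5, 1.0 and 1.5 points to the whole sample. It gave rank-sum rates of 3–6%, 32–34% and 75–80%.

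**Step 4. What the between-session test would do.** 6,000 trials, 10 per order, a true 2-point benefit, *e* = 1 and 60% use in both conditions.

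- Read as session 1 against session 2: half of each session's participants are on active, so treatment cancels. The mean difference is 0.0 and rejection is 0.1–0.5% (raw scores) or about 3% (changes).
- Read as active against sham: the difference is 2.0 and rejection is 70–90% (raw) or 82–83% (changes).

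**Step 5. A sham-controlled contrast.** For each person take the session 1 change minus the session 2 change, then compare the two orders by t-test.

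- No effect, equal use: the shift cancels, the difference is 0.0 and rejection is about 5%.
- True benefit of 1 point: power about 31% (27% with the rank-sum test). At 2 points: 82–83% (79%).
- True benefit of 1 point, *e* = 1, use 40% after active and 80% after sham: (1 + 0.4) − 0.8 = 0.6, and power falls to 14%.

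Under the second set of assumptions, a paired t-test of active change minus sham change stayed at 4.6–5.6% for shifts from 0 to 1.5 points.

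**Step 6. Effect on a later trial.** Assume a true benefit of 1 point, SD 2, two arms and 80% power. Per arm, n = 2(1.96 + 0.84)² × 2² / d² ≈ 62.8/d². Power at the true difference is Φ(√(n/2) × 1/2 − 1.96).

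| Fall used for sizing | n per arm | True power |
|---|---|---|
| 1.00 | 63 | 80% |
| 1.15 | 48 | 69% |
| 1.60 | 25 | 42% |
| 2.35 | 12 | 23% |

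**The case against.** **The real gap is the missing sham, not the painkillers.** The contrast would need the same correction if nobody took a painkiller. This is largely right, and it is why the main remedy is the contrast itself. Painkiller timing is still a distinct, protocol-made source of shift in a known direction.

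**The planned test seldom rejects falsely.** This stands for the low and middle cases, where three of the four rates are below 5%. It does not remove the bias in the estimate, and the protection comes from ignoring the pairing.

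**The size is assumed and partial.** This stands. The documents give no prevalence of use, analgesic effect or SD. Painkillers the evening before a session are allowed, and some surveys may be completed before that day's dose. The telephone script in Appendix G does not mention the session-day bar, although other instructions may exist.

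**A controlled comparison is already implied.** Section 11.1 declares an AB/BA crossover, and active against sham is a natural reading of the between-session test. That reading would supply the controlled contrast, but the text does not define it and it is not the stated hypothesis.

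**A same-day rating may simply be missing from the lists.** That is possible, since 11.1 refers to ratings before and after stimulation. Neither visit list includes one, however, and the follow-up survey is the rating described as assessing change in pain.

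**The sample-size consequence is speculative.** Section 11.2 does not say that the active-only fall would be used. The calculation shows what would follow if it were.

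**Conclusion.** The concern holds. Followed as written, the secondary hypothesis gives a pain change under active stimulation that mixes any tACS effect with resumed painkillers, regression to the mean and placebo response. Under the assumed ranges the painkiller part is 0.15 to 1.35 points, below the 2-point MCID. False rejection with the planned test is near or below 5% except at the extreme, but the estimate is biased throughout. Weight is minor to moderate: a secondary outcome in a 20-person pilot, with the primary HRV comparison unaffected. The correction should be made because it is cheap and the sham data are already collected. Confidence is medium, since the size rests on assumed painkiller use, painkiller effect and SD.

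**What to change.** In 2.4 and 11.1, define the secondary pain contrast as the within-person active-minus-sham difference in change from the pre-session DVPRS to the two-day DVPRS. Take each person's session 1 change minus session 2 change and compare active-first with sham-first participants, by t-test or by the rank-sum test already named. Report the estimate with a 95% confidence interval. Let this definition replace the undefined between-session test. State that a fall from baseline under active stimulation alone will not be read as a tACS effect or used to size later trials.

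Add one item on painkillers taken and time of last dose, before each session's DVPRS and in each two-day survey, reported by condition. Unequal use would still attenuate the contrast if less relief leads to more painkiller use. Optionally, ask participants to complete the survey before that day's painkiller, to match the session-day rule.

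The cost is a changed sentence in each of two sections, one item, and about a minute of participant time. No visit is added. The drawbacks are a pain result that may look less favourable, low power for a 1-point benefit (about 31% with 20 participants), and, if the optional timing is adopted, a delayed dose for some participants.
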